6 STUDY INTERVENTION

6.1 Study Product Description

The investigational devices used in this study as a permanent implant are Target XXL Detachable Coils and Target XL Detachable Coils (Stryker Neurovascular). Target Detachable Coils are stretch resistant, electrolytically detachable coils consisting of a platinum-tungsten alloy coil attached to a stainless-steel delivery wire. Target Detachable Coils are intended to endovascularly obstruct or occlude blood flow in vascular abnormalities of the neurovascular and peripheral vessels. In particular, these devices are currently indicated for endovascular embolization of intracranial aneurysms. Such coils are routinely used in clinical practice for neonatal embolization. However, they have not been previously used in a fetal intervention. More information about the products can be found in the product labeling.

Additional devices being used off-label during the investigational procedure include:

ASAHI Neurovasculature Guide Wire: ASAHI CHIKAI Black 18 Soft Tip (K171613)
Headway 21 Microcatheter, Model MC21250S (K093160)
Bard TruGuide Coaxial Biopsy Needle, 19Ga 17.8 cm, Model C2020A (K936194)

However, these devices are used during the procedure for the delivery of the implanted coils and are entirely removed from the subject at the end of the procedure.

6.1.1 *Acquisition*

The coils will be purchased directly from the manufacturer, Stryker Neurovascular.

6.1.2 *Formulation, Packaging, and Labeling*

The devices will be provided with the commercial label.

6.1.3 *Product Storage and Stability*

Prior to each procedure, the manufacturer will provide a supply of XL and XXL coils. These coils are stored in the Interventional Radiology area at BCH separately from the clinical stock.

6.2 Accountability Procedures for the Study Product

The product is for single use only. Once the procedure is over, any unused and unopened coils and leftover materials, including the detachment system and packaging will be returned back to the manufacturer. Each coil is individually labeled with a bar code, scanned in after the procedure for tracking purposes by Children's Hospital and the coil vendor (per standard clinical protocol for all intracranial coils deployed in patients).

6.3 Concomitant Medications/Treatments

Concomitant medications taken by the mother will be recorded only if they are directly related to any AE. This information will be abstracted from the medical record.

All concomitant medications taken by the neonate will be abstracted from the medical record from birth through discharge. After discharge, information on concomitant medications for the baby will be collected by asking the family during the follow up visits or phone calls.

For concomitant medications, the medication name, dose, indication, and start and stop dates will be recorded.

6.4 Study Procedural Intervention Description

The study involves a single fetal intervention of maternal transuterine, fetal transcranial torcular puncture and median prosencephalic vein embolization. Detachable platinum coils (Target XL and XXL Detachable Coil, Stryker Neurovascular) will be used to pack the prosencephalic varix. This procedure will take place in an OR at either Brigham and Women's Hospital or Boston Children's Hospital.

6.5 Administration of Procedural Intervention

Mothers will undergo epidural anesthesia and then be positioned with left uterine displacement. After induction of maternal regional analgesia, the location of the placenta and the fetal orientation will be established using conventional ultrasonographic techniques. External and/or transvaginal fetal manipulation will then be employed to produce an ideal, or nearly ideal, fetal position for transcranial torcular puncture and subsequent median prosencephalic vein embolization.

While it is impossible to continuously monitor fetal heart rate during the intervention, as the ultrasound signal emitted by the heart rate doppler monitor interferes with the ultrasound probe used for visualization of the fetal head, the fetal heart rate will be checked frequently throughout the procedure – at least every five minutes, as well as after positioning the fetus appropriately for the intracranial intervention, even if the heart rate was checked less than five minutes prior to the repositioning. In order to ensure that these fetal heart rate checks occur without fail, one team member will be designated to monitor a 5-minute timer throughout the case and call out to the team when the time to check the heart rate has arrived. A second team member will be tasked with turning on a hand-held heart rate monitor at that moment and calling out the fetal heart rate once a reading is obtained. After that, the ultrasound-guided procedure at the fetal head will continue.

If an ideal or near-ideal fetal position cannot be obtained within 40 minutes of transcutaneous and transvaginal fetal manipulation, no attempt to perform fetal VOGM embolization will be made, and the procedure will be terminated. If, in the judgment of the clinical team, the subject remains a viable candidate for intervention, another attempt at fetal embolization may be made on a separate day.

Once ideal fetal positioning has been achieved, prior to needle insertion through the fetal posterior skull, an intramuscular injection will be administered to the fetus to provide fetal analgesia and fetal immobility. The interventional procedure will proceed using fetal sonographic visualization.

[figure not shown]

Figure 1

After transcranial access to the torcular has been achieved using an 18 or 19G needle (red line in Figure 1 above), the needle hub will be attached to extension tubing connected to a continuous perfusion heparinized saline drip via a rotating hemostatic valve (RHV). A microcatheter (blue), attached to a second pressurized continuous perfusion heparinized saline drip, will be introduced via the RHV, and navigated over a 0.018" microwire from the torcular through the falcine or straight sinus into the median prosencephalic varix, using sonographic visualization.

For vascular structures *in vivo*, achievable packing densities of the total volume of the viscus using metallic coils are on the order of 15-25%. For brain aneurysms, where the goal is complete exclusion of the aneurysm dome from the arterial circulation in order to minimize the risk of rupture, densities of 20-25% are typically the goal [23]. In contradistinction, the goal in VOGM embolization of the varix is to achieve significant diminution in flow through the malformation rather than complete exclusion from the circulation. In fact, we calculated the packing density in six neonatal patients in whom successful coil embolization of the varix was carried out in order to alleviate heart failure and found that a packing density of 13-22% resulted in excellent clinical outcome. As such, our target packing density for the fetal interventional procedure, where the explicit goal is to reduce flow through the malformation and thereby increase the ratio of IT to NAR neonates, will be ~15%.

The number of detachable platinum coils (Target XL and XXL Detachable Coil, Stryker Neurovascular) needed to achieve a packing density of ~15% within the varix will be calculated using standard neurointerventional software designed for such calculations. The caliber of the prosencephalic varix will be measured along three axes on fetal MR, and overall volume calculated. The predetermined number of coils will be deployed within the varix under ultrasound (shown in green in Figure 1 above). Target XL and XXL are optimized for large and

giant brain aneurysms, have been chosen for a combination of relatively large diameter of coil filament, resulting in efficient packing, combined with increased softness, lowering the risk of iatrogenic trauma during deployment. Note that only one single session of deployment of coils will be performed per pregnancy as part of this study.

Color doppler ultrasound will be used to visualize flow and to characterize the waveform within the prosencephalic varix prior to and after embolization. In order to minimize the total Doppler exposure and thus thermal transfer, the field of view of the ultrasound probe will remain on the anatomic region being treated, the prosencephalic varix, and Doppler assessment of flow in the internal carotid arteries and circle of Willis will not be measured; the Thermal Index (TI) will be kept at less than 1.0. We anticipate up to approximately one hour of total ultrasound imaging, with the color and spectral Doppler involving less than 10-15 minutes of that time. This falls well under AIUM recommended maximum scanning time for TI of 1 (less than 60 minutes). In addition to the above thermal considerations, there is no a priori expectation of how the circle of Willis arterial flow velocity might change immediately as a result of the embolization, and thus no clinical or technical benefit accruing to the procedure.

In accordance with our fetal cardiac interventional experience, the entire procedure is expected to take <2 hours, which includes time for fetal positioning.

After embolization, mothers will be monitored either at BCH or at the Brigham and Women's Hospital until at least the morning after the procedure, or longer, if necessary. Fetal heart rate is monitored continuously after the procedure, and a focused ultrasound to check placenta, cervix, and the fetal brain will be performed 3-6 hours post-procedure. The measurement will conform to the AIUM official statement on measurement of fetal heart rate. Mothers will receive tocolytic medication perioperatively and continued for 12 hours (po). Continuation of tocolytics past 12 hours will be on an individualized basis, as determined by the maternal fetal specialist. A follow-up fetal echocardiogram, obstetric ultrasound including cervical length, and fetal MRI will be repeated 24-28 hours after the procedure. Maternal activity will be increased gradually, depending upon maternal symptoms and cervical ultrasound findings.

6.6 Procedures for Training of Clinicians on Procedural Intervention

The study procedure will be conducted by licensed clinicians. An obstetric anesthesiologist will administer the maternal anesthesia. The administration of the fetal intramuscular anesthetic and paralytic will be overseen by a fetal anesthesiologist credentialed at both BWH and BCH. A radiologist with ultrasound specialization and extensive experience with invasive fetal procedures will perform the fetal ultrasound throughout the procedure at BWH, while at BCH a maternal-fetal medicine specialist will provide ultrasound guidance. BWH and BCH maternal-fetal medicine credentialing includes the ability to perform invasive fetal procedures, and MFM physicians with experience with invasive fetal cardiac procedures and credentialed at BWH and BCH will be present and participate in each procedure, positioning the fetus and directing the transuterine needle transcranially into the fetal torcular. The microcatheterization and coil deployment will only be performed by [name], credentialed at both BWH and BCH.

7 STUDY SCHEDULE

7.1 Screening, Enrollment, and Baseline (Visit 1)

Screening

- Review medical history to determine eligibility based on inclusion/exclusion criteria.
- Review prior fetal ultrasounds, fetal echocardiography, and fetal MRI to determine eligibility based on inclusion/exclusion criteria.

Enrollment

- Obtain and document informed research consent from both parents of the fetal subject.

Baseline

- Perform a physical exam
- Obtain demographic information and medical history
- Perform fetal ultrasound, fetal echocardiogram, and fetal MRI

7.2 Study Intervention (Visit 2)

Study Procedure Visit

- Perform a preprocedure assessment on the mother
- Obtain clinical procedural consent and anesthesia consent
- Perform the study intervention

After the intervention

- Mothers will be monitored at least overnight at BWH or BCH, or longer if needed
- Tocolytic medication will be administered perioperatively and as needed for the first 12 hours post-intervention
- Fetal heart rate will be monitored continuously after the procedure
- Focused ultrasound to look at cervix, placenta and fetal brain will be performed 3-6 hours post-procedure
- Fetal ultrasound, fetal echocardiogram, and fetal MRI will be performed 24-28 hours after the procedure
- Fetal distress will be addressed clinically and as appropriate for gestational age and status of vein of Galen malformation
- Preterm labor, rupture of membranes and abruption will be addressed clinically, as appropriate for gestational age

7.3 Pre-Delivery Follow up visits

If more than 4 weeks remain before expected delivery, the following assessments will be repeated every 4 weeks until delivery:

- Fetal ultrasound, fetal echocardiogram, and fetal MRI

7.4 Delivery

Plans will be made for all subjects to be delivered at BWH. The mode of delivery is not impacted by the fetal intervention and will be determined based on clinical criteria. Likewise, gestational age of delivery will be determined clinically. Depending on the specifics of each case, including how far along the pregnancy is, how severely affected the fetus is, and other factors, in some cases, early delivery would be the chosen option, while in others, termination might be the recommended option, as previously discussed by the subject with the clinical care team. A recommendation of termination of pregnancy would result from major cerebral injury (intracranial hemorrhage other than petechial or parenchymal infarct >10% of the supratentorial brain volume) visualized on fetal imaging, in the setting of a gestational age young enough that termination remains an option. As such major cerebral injury is one of the unacceptable safety events mentioned above in Section 3.2 and below in Section 11.3, the subject in question would be included in the calculations related to the two-stage study design for safety. However, since fetal death would not have been spontaneous but rather by termination of pregnancy, the subject would not be counted towards the fetal deaths in the study.

If no such situation arises, elective delivery will be performed on a date chosen by the obstetrician as optimal in terms of safety for the mother and baby, in the same way that delivery dates are chosen for patients with vein of Galen malformations who do not undergo fetal intervention.

The newborn will be admitted to the NICU, as per the current practice for all patients with VOGM. As per clinical care, an MRI and echocardiogram will be performed as soon as possible after delivery, typically on day 1 of postnatal life. All care, including additional embolization procedures and additional imaging, will be done per standard of care for this patient population. Per our protocol (and similar to that of most major referral centers for VOGM), if a neonatal patient is unable to be extubated or is not stable enough on medications to be discharged from the NICU within a week due to cardiopulmonary failure, this indicates a need for urgent neonatal embolization.

At our center, extubation criteria in neonates without an underlying lung disease include:

- Patient awake with spontaneous and regular breaths, and
- Mean airway pressure on the ventilator < 10 cmH₂O and FiO₂ < 0.25
- Hemodynamical stability with normal heart rate and blood pressure

At our center, NICU discharge criteria include:

- Absence of respiratory difficulties with respiratory rate consistently under 60/min and without any periodic breathing
- Feeding well (bottle or breast feeding) with good weight gain
- Maintaining temperature in open crib

There are no study-specific requirements or procedures at this point, but data will be collected regarding the subjects' medical care and any adverse events that occur while inpatient in the NICU.

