3.2 Study Outcome Measures

Primary (safety) endpoint: The procedure is deemed safe if

- 1) **None** of the following unacceptable events occur within 7 days of fetal embolization:
 - a) Fetal death
 - b) Fetal intracranial hemorrhage, either parenchymal or extra-axial, other than petechial hemorrhage. A petechial hemorrhage is seen as focal staining of the brain parenchyma by blood products on MRI, is not associated with mass effect, and there are minimal neurologic sequelae. Petechial hemorrhages are usually considered non-serious adverse events in trials.
 - c) Maternal death
- 2) **None** of the following unacceptable events occur between fetal embolization and delivery:
 - a) Intra-procedural and post-procedural morbidity to the fetus and mother, probably related to the fetal intervention, e.g. placental abruption with subsequent sequelae
 - b) Preterm delivery < 28 weeks, probably related to the fetal intervention
 - c) Maternal blood transfusion or unanticipated surgical intervention, probably related to the fetal intervention
 - d) Presence of fetal imaging evidence of new brain injury in a location or pattern unexpected for the natural history of vein of Galen malformation, probably related to the fetal intervention

Secondary (efficacy) endpoint: The procedure is deemed efficacious if **none** of the following serious postnatal events occur within 30 days of birth:

1. Urgent neonatal embolization is needed. Without fetal intervention, we'd expect 80% of the cohort to require such intervention.
2. Neonatal death. Without fetal intervention, we'd expect a mortality rate of 40% in this cohort.
3. Brain MRI within the first three weeks after birth reveals parenchymal brain injury (acute infarct or gliosis) affecting > 10% of the supratentorial brain volume. Without fetal intervention, we'd expect 30% of patients in this cohort to show this kind of injury.

Additional efficacy data to be collected includes assessment of the neurocognitive development in the treated cohort. Subjects will be followed and assessed until age 24 months and results will be compared to historical controls of NAR VOGM patients treated using the current neonatal paradigm.

Comparison of outcomes will be made with published (meta-analysis and UK national data [1, 2, 6, 7]) and institutional historical results for fetuses who receive standard neonatal or post-neonatal treatment.

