11.3 Safety Review

Two-stage design for safety endpoint

In Stage 1, up to 11 evaluable patients will be enrolled (**Table 2**). Out of 11 patients, if 3 or more patients experience an unacceptable event (see definition in Section 3.2 above and recapitulated below Table 2), the intervention is unsafe and not worthy of further study. If 2 or fewer experience any unacceptable event, the trial will proceed to Stage 2, where an additional 9 evaluable patients will be enrolled, for a total of $N=20$ evaluable patients. Out of $N=20$ patients, if 4 or more patients experience any unacceptable event, the intervention is unsafe and not worthy of further study. If 3 or fewer patients experience any unacceptable event, the intervention is sufficiently safe and worthy of further study. In addition, in case of a single maternal death, the study will be halted pending review by the DSMB and the FDA.

This design tests the null hypothesis that the rate of unacceptable events is $P > 30\%$ versus the alternative that $P < 5\%$. The total type I error rate is 0.097 and the power is 97.5%. If the intervention is truly unsafe, there is a 68.7% probability of early trial termination.

Table 2: Decision rules for safety based on the optimum two-stage design.

	Cumulative number of patients with unacceptable events	Decision
Stage 1: Enroll 11 patients	3 or more	Terminate the trial: agent not worthy of further study
	2 or fewer	Inconclusive result: proceed to Stage 2
Stage 2: Enroll 9 additional patients	4 or more	Terminate the trial: agent not worthy of further study
	3 or fewer	Trial concludes: agent worthy of further study

- 1) Unacceptable events within 7 days of fetal embolization include:
 - a) Fetal death
 - b) Fetal intracranial hemorrhage, either parenchymal or extra-axial, other than petechial hemorrhage. A petechial hemorrhage is seen as focal staining of the brain parenchyma by blood products on MRI, is not associated with mass effect, and there are minimal neurologic sequelae. Petechial hemorrhages are usually considered non-serious adverse events in trials.
 - c) Maternal death
- 2) Unacceptable events occur between fetal embolization and delivery include:
 - a) Intra-procedural and post-procedural morbidity to the fetus and mother, probably related to the fetal intervention, e.g. placental abruption with subsequent sequelae
 - b) Preterm delivery < 28 weeks, probably related to the fetal intervention

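### Section 7.4 counts major fetal brain injury followed by termination as a primary safety event with no condition on timing, pattern or relatedness, but the lists in 3.2 and 11.3 leave such injury out when it is not judged probably related (hemorrhage only after Day 7), and 11.5 gives a third window

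*Combined protocol and SAP*

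**What the plan says.** **Section 7.4 (Delivery)** defines the trigger for a termination recommendation as "major cerebral injury (intracranial hemorrhage other than petechial or parenchymal infarct >10% of the supratentorial brain volume) visualized on fetal imaging". It puts no day limit, pattern condition or relatedness condition on that injury. It then asserts that the injury is already on the endpoint lists ("As such major cerebral injury is one of the unacceptable safety events mentioned above in Section 3.2 and below in Section 11.3") and concludes that "the subject in question would be included in the calculations related to the two-stage study design for safety". Because the death would not be spontaneous, "the subject would not be counted towards the fetal deaths in the study".

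**Sections 3.2 and 11.3** give the same two lists.

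- List 1 requires that none "of the following unacceptable events occur within 7 days of fetal embolization". Item 1(b) is "Fetal intracranial hemorrhage, either parenchymal or extra-axial, other than petechial hemorrhage", with no relatedness condition.
- List 2 runs from embolization to delivery. Item 2(a) covers fetal or maternal morbidity that is probably related to the intervention. Item 2(d) covers "new brain injury in a location or pattern unexpected for the natural history of vein of Galen malformation, probably related to the fetal intervention".
- Neither list names an infarct above 10% of supratentorial volume.

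**Section 11.5** says the safety endpoint is observed from Day 0 to Day 7 after the intervention.

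**Section 7.3** repeats fetal ultrasound, echocardiogram and MRI every 4 weeks until delivery if more than 4 weeks remain, so injury after Day 7 can be detected.

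**The concern.** The primary endpoint is a count of patients with an unacceptable event, and the plan tells the reader in three places, in three ways, which prenatal brain injuries enter it. Section 7.4 relies on 3.2 and 11.3 for a rule that those sections do not contain.

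The affected subject is the one for whom the count matters most: a fetus with a major brain injury whose pregnancy is then ended. Section 7.4 keeps that subject out of the fetal deaths. With no live birth there can be no postnatal event under the efficacy definition. If the injury is also off the safety lists, the subject contributes no adverse outcome to either decision rule. Section 7.4 shows that the sponsor intended the opposite for safety.

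The boundaries are tight (3 of 11, 4 of 20), so two people applying different sections to the same data could reach opposite decisions on continuing.

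**Working it through.** **Step 1. Set the rules side by side.** Take major cerebral injury as 7.4 defines it, in a subject whose pregnancy is then terminated.

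| Injury | Judged probably related? | 7.4 | 3.2 and 11.3 | 11.5 window |
|---|---|---|---|---|
| Non-petechial hemorrhage, by Day 7 | either | counts | counts, 1(b) | inside |
| Non-petechial hemorrhage, after Day 7 | yes | counts | counts, 2(a) | outside |
| Non-petechial hemorrhage, after Day 7 | no | counts | **does not count** | outside |
| Infarct >10%, expected pattern | yes | counts | counts, 2(a) | inside only to Day 7 |
| Infarct >10%, expected pattern | no | counts | **does not count** | inside only to Day 7 |

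Item 2(d) needs both an unexpected location or pattern and a probable relation, so it does not rescue either bold row. Section 11.5 read literally would also drop later events that 2(a) and 2(d) include.

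**Step 2. Reproduce the stated design.** Inputs from 11.3: stop if 3 or more of 11 have an event; unsafe if 4 or more of 20; null 30%, alternative 5%. With p the probability that a patient counts as having an event,

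P(declare safe) = Σ over x = 0, 1, 2 of P[Bin(11, p) = x] × P[Bin(9, p) ≤ 3 − x].

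- p = 0.30: 0.0198 × 0.7297 + 0.0932 × 0.4628 + 0.1998 × 0.1960 = 0.0144 + 0.0431 + 0.0392 = 0.0967 (stated type I error 0.097).
- p = 0.05: 0.5684 + 0.3266 + 0.0805 = 0.9755 (stated power 97.5%).
- Early stop at p = 0.30: P[Bin(11, 0.30) ≥ 3] = 0.6873 (stated 68.7%).

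All three figures reproduce. The arithmetic of the design is sound; what is unsettled is which patients it counts.

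**Step 3. One subject.** Reclassifying one patient moves 2 of 11 to 3 of 11 (continue becomes stop), or 3 of 20 to 4 of 20 (safe becomes unsafe).

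**Step 4. Sensitivity to the definition.** The documents give no rate for the disputed events, so q percentage points is an assumption.

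| q (assumed) | Rate is 30% under 7.4, lists count 30 − q | P(declare safe) | Rate is 5% on the lists, 7.4 counts 5 + q | P(declare safe) |
|---|---|---|---|---|
| 0 | 30% | 9.7% | 5% | 97.5% |
| 2 | 28% | 13.3% | 7% | 93.6% |
| 5 | 25% | 20.6% | 10% | 84.0% |
| 10 | 20% | 38.2% | 15% | 61.3% |

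The left half shows the false reassurance if the wider count is the right one and the lists are used. The right half shows the cost in power if the count is widened while the hypotheses stay at 30% and 5%.

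**The case against.** The strongest reply has four parts.

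- **Item 2(a) already reaches to delivery.** A reader might infer that the lists never count hemorrhage after Day 7, or count infarct only when its pattern is unexpected. The documents do not support that: 2(a) takes in either one if it is probably related. This part stands and confines the gap to injury not judged probably related. It does not close the gap. Sections 2.1.2 and 2.2 describe bihemispheric injury as part of VOGM itself, and 8.3.1 treats an established alternate etiology as pointing to not related. An expected-pattern infarct therefore always has another explanation available, and attribution in a single-arm trial of 20 is weak.
- **Section 7.4 is a loose cross-reference, not a second definition.** Its counting sentence concerns only the subject for whom termination is recommended. The limit on scope is fair. But the sentence states a counting rule for the primary endpoint and grounds it on lists that lack the event, so one of the texts has to change.
- **The relatedness condition in list 2 is deliberate.** The disease causes fetal brain injury, and a procedural safety endpoint may reasonably exclude natural history. This stands. A reader might infer that all such injury must count regardless of attribution, with or without termination. The documents do not require that, and the right half of the table shows it would not be free.
- **The events are not lost.** New parenchymal injury and non-petechial hemorrhage are exploratory outcomes in 3.2, and Section 9 sends all serious adverse events to the DSMB. True, but neither route settles whether the patient counts toward 3 of 11 or 4 of 20.

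**Conclusion.** The plan is wrong as written: 7.4 says the lists in 3.2 and 11.3 contain an event that they contain only in part, and 11.5 contradicts the whole of list 2. The dispute is confined to hemorrhage after Day 7, or infarct above 10% in an expected pattern, that is not judged probably related and is followed by termination. That subject is a safety event under 7.4, is not one under 3.2 or 11.3, is excluded from fetal deaths, and cannot have a postnatal event.

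One such subject can reverse either safety decision; that follows from the boundaries alone. The shifts in probability (9.7% to 20.6% or 38.2%; 97.5% to 84.0% or 61.3%) rest on an assumed 5 or 10 points and illustrate sensitivity; they are not estimates. A reader might also infer that the stated type I error or power is miscalculated. It is not: both reproduce for whatever event the rate p describes.

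This should be settled before the Stage 1 decision because it defines the primary count and a stopping boundary. No view is taken on the termination criterion itself.

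**What to change.** Reconcile 3.2, 7.4, 11.3 and 11.5 into one counting rule before the Stage 1 decision. At minimum:

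1. In 3.2 and 11.3, state what 7.4 already intends: a subject whose pregnancy ends by termination after major cerebral injury as defined in 7.4 counts once as a patient with an unacceptable event.
2. In 11.5, state that the observation window is 7 days for list 1 and runs to delivery for list 2.
3. State explicitly whether the same injury without termination counts regardless of attribution. This is the sponsor's choice. If it is added, report the effect on the operating characteristics and revisit the 30% and 5% hypotheses. For example, P(declare safe) falls from 97.5% to 84.0% if an assumed 5 points are added to the 5% rate.

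Items 1 and 2 cost a few lines of text and no new data, since fetal imaging to delivery is already scheduled. They need not lengthen the Stage 1 pause, because 11.5 already allows enrollment to be suspended until Day 30 of life of the most recently treated patient. The price of item 1 is that some natural-history injury ending in termination will count against the procedure, as 7.4 already accepts.
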